3.7.2.4 Failure-free-survival (FFS)

FFS is defined as the absence of new cGVHD systemic therapy, non-relapse mortality and recurrent malignancy (i.e., underlying disease) and is censored by last response assessment or long term follow up assessment, whichever is the latest and available. Kaplan-Meier plots, descriptive statistics of FFS and landmark FFS at 6, 12, 18, 24, 30 and 36 months will be provided. In addition, analyses for the three components of FFS will also be provided.

3.7.2.5 Overall Survival (OS)

OS is defined as time from first dose of belumosudil to the date of death due to any cause and is censored by last response assessment or long term follow up assessment, whichever is the latest and available. Kaplan-Meier plots, descriptive statistics of OS and landmark OS at 6, 12, 18, 24, 30, 36 months will be provided.

3.7.2.6 Percentage of subjects who have a best response of PR and percentage of subjects who have a best response of CR

The percentage of subjects who have a best response of PR and percentage of subjects who have a best response of CR will be summarized separately by treatment groups.

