At 3 months after Baseline and every 3 months thereafter ( $\pm$  14 days), subjects will report to the clinic for the same efficacy and safety assessments and dispensing of belumosudil at Baseline. (Height is only required at Baseline.) The study drug diaries for the past 3 months will be collected, and new study drug diaries dispensed. Any remaining belumosudil will be collected.

Subjects may receive belumosudil on Study KD025-217 for up to an additional 2 years, at the discretion of the Investigator (and with guidance from the medical monitor), beyond what they had received in Study KD025-208 or Study KD025-213, cGVHD progression, or unacceptable toxicity.

Efficacy and safety endpoints are described in Section 6.3 and Section 6.4, respectively.

Subjects will return to the clinic for a 28-day Follow-up Visit at 28 days (± 7 days) after the last dose of study drug. Subjects will have LFTU approximately every 3 months until an FFS event occurs. After the 28-day Follow-up Visit has been completed, subjects will be contacted approximately every 3 months by telephone, e-mail, or postal mail to confirm survival status, any initiation of new systemic cGVHD therapies, and relapse of underlying disease. Alternatively, this information may be obtained from the subject's medical records. The Schedule of Assessments is presented in Appendix A: Schedule of Assessments.

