### 6.3 Efficacy Endpoints

The efficacy endpoints of this study will be:

- Duration of Response (DOR)
- Change in LSS (Appendix D: Lee cGVHD Symptom Score)

- Time to Next Treatment (TTNT): defined as the time from the first dose of belumosudil to the start of additional systemic cGVHD therapy
- FFS: defined as the absence of cGVHD treatment change, non-relapse mortality, and recurrent malignancy
- Overall Survival (OS): defined as the time from first dose of belumosudil to the date of death due to any cause
- Percentage of subjects who have a best response of CR and percentage of subjects who have a best response of PR
- Response by individual organ
- Change in corticosteroid dose: the change in prednisone equivalent dose of corticosteroids (mg/kg/day) during the study
- Change in cGVHD Global Severity Rating using the Clinician-reported Global cGVHD Activity Assessment (Appendix B: Clinician-reported Global cGVHD Activity Assessment)

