#### 9.6 Interim Analysis

An interim analysis will be performed when all subjects have completed at least 3 years of treatment with belumosudil or withdrew earlier (not inclusive of the companion study subjects).

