3.1.4 Study Day

The study day for all assessments prior to the first study drug administration is calculated as the difference between the date of the measurement (e.g., assessment date, sample collection date, etc.) and the start date of study treatment. The day before the start of study treatment is Study Day -1.

The study day for all post assessments after the first study drug administration is calculated as the difference between the date of the measurement (e.g., assessment date, sample collection date, etc.) and the start date of study treatment in parent study KD025-208/KD025-213, plus one day. The first day of study treatment is Study Day 1.

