3.1.5 Baseline

Baseline value for efficacy analyses is defined as the valid and last non-missing value obtained within 28 days prior to subject receiving the first study medication in parent study KD025-208/KD025-213.

Baseline value for safety analyses is defined as the "Baseline" visit from KD025-217.

Baseline can be the day before the first study medication or on the same day as the first study medication if a pre-dose assessment is available. Subjects without data on a parameter before the first study medication will have a missing baseline for this parameter.

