3.7.2.3 Time to Next Treatment (TTNT)

The TTNT will be measured as the time from first treatment to the time of new systemic cGVHD treatment (which will be defined by clinical team review), censored by last response assessment or long term follow up assessment, whichever is the latest and available. TTNT will be analyzed

Kadmon Corporation

Page 17 of 26

by the Kaplan-Meier survival method as well as the landmark analysis at 6, 12, 18, and 24 months.

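### Overall survival is timed from the first parent-study dose but analysed only in KD025-217 enrolees without delayed entry, so its landmark rates are biased upward as rates from first dose; TTNT and FFS share the structure, with size unknown

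*SAP*

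**What the plan says.** **Endpoints and origins.** SAP 3.7.2.5: "OS is defined as time from first dose of belumosudil to the date of death due to any cause". Protocol 6.3 gives the same origin for OS and describes TTNT as "defined as the time from the first dose of belumosudil to the start of additional systemic cGVHD therapy". SAP 3.7.2.3 starts TTNT at first treatment. Neither document gives an origin for FFS.

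**Method.** OS and FFS get Kaplan-Meier plots. For FFS, "landmark FFS at 6, 12, 18, 24, 30 and 36 months will be provided", and OS has the same six landmarks. TTNT is analysed "by the Kaplan-Meier survival method as well as the landmark analysis at 6, 12, 18, and 24 months". The only rule on observation time is right-censoring at the last response or long-term follow-up (LTFU) assessment.

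**Population.** SAP 3.2 puts all efficacy analyses on the Full Analysis Set, meaning everyone enrolled in KD025-217. Protocol 9.3 agrees.

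**Entry.** Under Protocol 4.3 a subject must be on belumosudil in a parent study, be in LTFU (which ends at an FFS event), or be a Companion Study adult with at least 6 months of treatment or in LTFU.

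**The concern.** A subject enters KD025-217 only after surviving from first dose to entry. If the survival clock starts at first dose, ordinary Kaplan-Meier puts that subject in the risk set during a period in which the subject's death was impossible. Deaths among parent-study subjects who never reached KD025-217 are absent from both numerator and denominator. This is left truncation, and the plan has no step for it.

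Long-term efficacy is part of the study's single objective, and these landmark rates are its time-to-event summary. A 24-month OS taken from these tables would read as survival from starting belumosudil, while part of it would be fixed by the eligibility rules.

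**Working it through.** **1. Which first dose?** No section says parent study for these endpoints. Four places point there:
- SAP 3.1.4 counts study day after dosing from the "start date of study treatment in parent study KD025-208/KD025-213, plus one day".
- SAP 3.1.5 takes the efficacy baseline as a value "obtained within 28 days prior to subject receiving the first study medication in parent study KD025-208/KD025-213".
- Subjects who enter in LTFU have only LTFU contacts in KD025-217 (Protocol 6.2.2 and 6.2.5). They are in the Full Analysis Set but receive no KD025-217 dose, so an origin at a KD025-217 dose is undefined for them.
- Protocol 9.6 sets the interim analysis "when all subjects have completed at least 3 years of treatment with belumosudil or withdrew earlier", and SAP 3.6 tabulates exposure beyond 36 months. Protocol 3.1 says "Subjects may receive belumosudil on Study KD025-217 for up to an additional 2 years", so neither can be reached within KD025-217 alone.

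**2. Crude death rate.** The plan states no expected survival, so there is no figure of its own to reproduce. Inputs are from Protocol 1.4.1 and 1.4.2 at the 19 February 2020 cutoff: 11 deaths in 54 subjects with median follow-up 28.8 months, and 8 deaths in 132 with median 7.9 months. Medians stand in for means (assumption).

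- Person-months: 54 × 28.8 + 132 × 7.9 = 1,555.2 + 1,042.8 = 2,598
- Rate: 19 / 2,598 = 0.00731 per month (exact Poisson 95% interval 0.0044 to 0.0114)
- By study: 11 / 1,555.2 = 0.0071 and 8 / 1,042.8 = 0.0077, which agree

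**3. Formula.** With constant hazard r and entry at E months, survival from first dose is S(t) = exp(−rt). Ordinary Kaplan-Meier among those alive at E reads 100% for t ≤ E, and exp(−r(t − E)) afterwards.

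**4. Results at r = 0.00731.**

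| Landmark | From first dose | Reads if E = 6 | Reads if E = 18 | Reads if E = 24 |
|---|---|---|---|---|
| 6 months | 95.7% | 100% | 100% | 100% |
| 24 months | 83.9% | 87.7% | 95.7% | 100% |
| 36 months | 76.9% | 80.3% | 87.7% | 91.6% |

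The bias at 24 months is 87.7 − 83.9 = +3.8 points for E = 6 and 100 − 83.9 = +16.1 for E = 24 or later. At 36 months it is about +3 to +15.

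**5. Uncertainty in the rate, 24 months.**
- r = 0.0044, E = 6: 92.4 − 90.0 = +2.4 points
- r = 0.0114, E ≥ 24: 100 − 76.0 = +24.0 points

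If true person-time is 25% lower or higher, 24-month survival from first dose is 79.1% or 86.9%, which lies within the same range.

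**6. What the documents say about E.** Protocol 4.3 names an amendment of 01 June 2020, so entry under that text cannot be earlier. The last KD025-213 first visit was about 6 months before 19 February 2020 (Protocol 1.4.2), taken as 19 August 2019. Main-part KD025-213 subjects were then at least 9.4 months from first visit on 01 June 2020 (9.0 from first dose if the 2-week screening is subtracted), and 24.7 months on 08 September 2021, the Amendment 1 date in SAP 1. On-treatment Companion adults need at least 6 months of treatment. For these groups 6-month OS is 100% by construction. Subjects entering early from LTFU under the parent amendment are a possible exception.

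**7. Selection.** About 70 enrolees are 70/186 = 37.6% of the 54 + 132 parent-treated subjects, or 70/206 = 34.0% with the 20 planned Companion adults. The 19 deaths recorded by February 2020 cannot appear.

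**The case against.** **The rates are true of the enrolees.** All of them did survive to entry, the study has no formal hypothesis (Protocol 9.1), and the SAP does not claim to estimate survival for all treated subjects. It stands that no error rate is affected. But nothing in SAP 3.7.2.3 to 3.7.2.5 labels the rates as conditional. With entry times that differ between subjects, the ordinary curve is not survival conditional on any one time point either.

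**TTNT and FFS are less clear than OS.** This stands. A reader might infer that these curves must stay near 100% up to entry whatever the hazard. The documents do not support that. Pre-entry freedom from an FFS event is explicit only for LTFU entrants; for subjects still on drug it is implied. SAP 3.7.2.8 counts any corticosteroid rise to 0.9 mg/kg or more as new systemic therapy, which could create earlier events in active entrants. SAP 3.7.2.3 also leaves new treatment to clinical team review.

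**The size cannot be pinned down.** This also stands. A reader might take one bias figure, or a projected curve and numbers at risk for the whole enrolled group, as established. Either would need entry windows and a mix of parent studies that the documents do not give. The 36-month figures also extend a constant hazard well past KD025-213's median follow-up of 7.9 months.

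**Progression stops are not a separate loss.** A reader might add the 38 subjects who stopped treatment for progression (22 + 16) to the 19 deaths as further exclusions. The overlap is not reported, and stopping does not bar entry unless an FFS event followed.

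**Conclusion.** The point holds for OS. Following the SAP as written gives landmark rates that are biased upward as survival from first dose, because death-free time before entry is counted as time at risk. The parent-study origin is inferred, but the alternative leaves LTFU entrants without a start date.

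The illustrative 24-month bias is +4 to +16 points at the crude rate, and about +2 to +24 over its 95% interval. It rests on a constant hazard, medians used as means, assumed entry at 6 to 24 months or later, and entry not otherwise related to prognosis.

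TTNT and FFS have the same structure. The direction there is probably upward, the size is unknown, and FFS also lacks a time origin. The harm is to descriptive estimates only, but those are what this study reports, so the rule should be changed before the tables are produced.

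**What to change.** 1. State the time origin for OS, TTNT and FFS.
2. For the enrolee tables, use delayed-entry Kaplan-Meier with each subject entering the risk set at the KD025-217 consent date. Alternatively, present time from KD025-217 entry with landmarks after entry (for example 12 and 24 months), as an added or replacement analysis.
3. List subjects with a pre-entry FFS or TTNT event and leave them out of that endpoint's risk set.
4. Label the rates as conditional on status at entry, show numbers at risk, and drop landmarks with almost nobody at risk.
5. If rates from first dose are wanted, compute them on all parent-treated subjects with KD025-217 follow-up appended, as a supplementary analysis where those data can be used. Add a sensitivity analysis for informative censoring of subjects who did not enrol.

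Delayed entry does not recover unconditional rates. It gives survival conditional on reaching the earliest entry time, and if everyone entered after 24 months nobody is at risk at the 6- to 24-month landmarks. Time from entry avoids empty early risk sets but answers a different question.

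**Cost.** SAP text and modest programming; parent first-dose dates are already needed for study day. The early figures will be less favourable and less precise. Moving the origin to entry departs from the endpoint definitions in Protocol 6.3, and using all parent-treated subjects departs from the population in Protocol 9.3, so either change must be documented.

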#### 4.6 Withdrawal Criteria

Subjects will receive belumosudil treatment until clinically significant progression of cGVHD (defined as progression requiring addition of new systemic therapy for cGVHD), histologic recurrence of underlying malignancy, unacceptable toxicity, Investigator decision, subject preference/withdrawal of consent, loss to follow-up, Sponsor decision, or death (whichever occurs first).

Subjects who experience cGVHD progression as defined by NIH criteria but for whom no new systemic therapy is planned may continue to receive belumosudil and be assessed again at their next visit. If progression per NIH criteria is not confirmed or no new systemic therapy is planned, subjects may continue on belumosudil at the Investigator's discretion until subjects fulfill at least 1 criterion requiring discontinuation of study drug.

Belumosudil may be tapered after a sustained response for 6 months and cessation of all other immunosuppressants for at least 3 months. The tapering schedule for belumosudil is described in Dosage and Administration 5.2.

Subjects may be withdrawn from study treatment at any time by the Investigator or the Sponsor if it is considered detrimental for the subject to continue in the study. The reason for withdrawal will be captured in the eCRF.

Subjects have the right to withdraw from the study at any time and for any reason without prejudice to their future medical care by the physician or at the institution. If the subject wishes to voluntarily withdraw from the study, the physician will consult with the subject regarding procedures for safe withdrawal. Every effort should be made to have such subjects attend protocol visits including the 28-day Follow-up Visit. Reasons for withdrawal of consent will be captured in the eCRF. Subject data up to withdrawal of consent will be included in the analysis of the study, and where permitted, publicly available data can be included after withdrawal of consent.

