### 6.2.4 28 Day Follow-Up Visit

This 28-day Follow-up Visit (± 7 days) will be 28 days after the last dose of belumosudil.

Subjects will have the following assessments and procedures:

- Collection of any remaining belumosudil from subject
- Collection of study drug diary
- Use of corticosteroid dosage
- Use of other cGVHD therapies

- Symptom-directed PE
- Vital signs
- Weight
- KPS
- Hematology lab testing
- Clinical chemistry lab testing
- 12-lead ECG
- Urine pregnancy test (any positive results will be confirmed with serum testing)
- Use of concomitant medications
- AEs

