3.1.6.2 Missing event dates

Event date will be imputed only when day is missing, and the purpose of imputing an event date is to most conservatively calculate time to event. If the day is missing, the first (mid, last) day of the month will be imputed for undesired (neutral, desired) event. If the missing day is the same as the month of first dose of study drug, then the first dose date will be imputed for undesired event. These data imputations are for time to event calculation only and will not be used in the listings.

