3.7.2 Secondary Efficacy Endpoints

3.7.2.1 Duration of Response (DOR)

DOR will be presented according to 5 methodologies:

- The primary definition of DOR is the time from first documentation of response to the time of first documentation of deterioration from best response (e.g., CR to PR, or PR to LR).
- The secondary definition of DOR is the time from first documentation of response to the time of first documentation of lack of response.
- The tertiary definition of DOR is the time from first documentation of response to the time of initiation of new systemic cGVHD therapy.
- The quaternary definition of DOR is the time from first documentation of response to the time of first documentation of lack of response (as the secondary definition) but with durations summed for multiple response/lack of response episodes.
- The FDA definition of DOR is the time from first documentation of response to the time
 of first documentation of organ-level progression, initiation of a new cGVHD therapy, or
 death from any cause, whichever occurs first

The DOR will be reported for early responders, and statistics will include:

- Kaplan-Meier plots and descriptive statistics of DOR. The censoring rules in Table 2 will be applied
- Landmark analyses: Number and percentage of subjects with response sustained for ≥ 3, ≥ 6, ≥ 9, ≥ 12, ≥ 15, ≥ 18, ≥ 24, ≥ 30, ≥ 36 months

Table 2 Censoring Rules for Duration of Response

DOR	Events	Censoring		
Primary	 Deterioration from best response Initiation of new systemic therapy for cGVHD Death 	 Last documented response assessment If LR or initiation of new systemic therapy happens 		

Kadmon Corporation

Page 15 of 26

Secondary	 Documented LR Initiation of new systemic therapy for cGVHD Death 	immediately after two or more missed response assessments, the event date is set as 24 weeks after last documented response assessment prior this event
Tertiary	 Initiation of new systemic therapy for cGVHD Death 	Last response assessment or long term follow up assessment, whichever is the latest and available
Quaternary	 Documented LR Initiation of new systemic therapy for cGVHD Death With summation of DOR from multiple response episodes 	Same as censoring rules for primary and secondary

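### Censoring for TTNT, FFS and OS leaves out the 28-day Follow-up Visit, and a missing event day can be imputed to before a documented event-free visit

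*SAP*

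**What the plan says.** **Censoring.** SAP 3.7.2.5 has OS "censored by last response assessment or long term follow up assessment, whichever is the latest and available". SAP 3.7.2.4 says FFS "is censored by last response assessment or long term follow up assessment, whichever is the latest and available", and SAP 3.7.2.3 does the same for TTNT. None of the three mentions a last date known alive or event-free from another source.

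**Contacts.** On treatment, response is assessed "At 3 months after Baseline and every 3 months thereafter" (Protocol 3.1). After treatment stops, Protocol 6.2.4 states: "This 28-day Follow-up Visit (± 7 days) will be 28 days after the last dose of belumosudil". That visit includes examination, vital signs, laboratory tests, ECG, adverse events and a record of cGVHD therapies, but no response assessment; Table 7 in Appendix A agrees. For subjects dosed in this study, Protocol 6.2.5 starts LTFU only once that visit is complete.

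**Missing event day.** SAP 3.1.6.2: "the first (mid, last) day of the month will be imputed for undesired (neutral, desired) event". The only floor is the month of first dose, where "then the first dose date will be imputed for undesired event".

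**Withdrawn subjects.** Protocol 4.6: "where permitted, publicly available data can be included after withdrawal of consent". The SAP does not say whether or how such data are used.

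**The concern.** Kaplan-Meier estimation needs survivors and failures to be observed over the same window. Here a death or new therapy between the last quarterly visit and the 28-day visit counts on its own date, but a subject seen event-free at that visit gets no credit for the same time. The risk set is thinned on one side only.

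The imputation rule is a separate fault. It can give an event date that the trial's own records contradict.

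The public-data sentence leaves a third opening. A withdrawn subject found dead could become an OS event, while one not found dead stays censored at the last assessment.

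OS, FFS, TTNT and DOR are main efficacy outputs of this uncontrolled study of about 70 subjects, with OS and FFS landmarks to 36 months.

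**Working it through.** The plan gives no expected OS, event target or power, so there is no stated figure to reproduce.

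**1. Which contacts extend follow-up**

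| Contact | Subject's status known | Extends censoring date |
|---|---|---|
| Quarterly clinic visit | yes | yes (response assessment) |
| 28-day Follow-up Visit | alive; cGVHD therapies recorded | no |
| LTFU contact | yes | yes |

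**2. Days lost**
- Dosing stops at a quarterly visit, and the 28-day visit is the last contact: 28 ± 7 = 21 to 35 days.
- Worst case, with dosing to the end of the next visit window and that visit's response assessment not done: 91 + 14 + 28 + 7 = 140 days.

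**3. Effect of the censoring rule on OS**

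Parent-study death rates (Protocol 1.4.1 and 1.4.2), using median follow-up as a rough stand-in for mean follow-up:
- KD025-208: 11 / (54 × 28.8/12) = 11/129.6 = 0.085 per year.
- KD025-213: 8 / (132 × 7.9/12) = 8/86.9 = 0.092 per year.

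Assumptions: exponential death at 0.05, 0.09 or 0.15 per year; cut-off uniform over 30 to 60 months from first dose; contacts every 3 months; 400,000 simulated subjects. Deaths by cut-off C keep their date. Survivors are censored at C (reference) or at 3 × floor(C/3) (SAP rule).

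| Hazard per year | Reference 36-month OS | SAP rule | SAP rule, one contact missed |
|---|---|---|---|
| 0.05 | 86.1% | 86.0% | 85.6% |
| 0.09 | 76.3% | 76.1% | 75.4% |
| 0.15 | 63.7% | 63.5% | 62.6% |

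Before rounding, the shortfalls are 0.1 to 0.3 points, and 0.5 to 1.2 with a missed contact. The simulation applies the lag to every survivor, not only to those last seen at the 28-day visit.

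**4. Day imputation**
- Example: first response documented on 20 June, and new systemic therapy recorded only as June. The imputed date is 1 June, so DOR = 1 June − 20 June = −19 days.
- If death falls evenly over the 91 days after the last contact, about 15% of deaths with a missing day are dated before a contact at which the subject was alive, by 10 days on average and 29 at most.

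**5. Public records, if only deaths were taken**

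Assumptions: exponential death and withdrawal; cut-off uniform over 3 to 5 years; every later death found; survivors censored at the earlier of withdrawal and cut-off.
- Withdrawal possible from first dose: at death 5% and withdrawal 10% per year, 36-month OS is 84.2% against a true 86.1% (1.9 points low). At 8% and 20% it is 73.2% against 78.7% (5.5 points low).
- Death and withdrawal possible only after entry at month 24: 0.2 points low and 0.7 points low for the same two settings.

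The second case is closer to this trial, because the Full Analysis Set holds only subjects enrolled in KD025-217. From the parent cut-off (19 February 2020) to the protocol amendment cited in the SAP (08 September 2021) is about 18.6 months. If entry was near that date, it falls around month 28.8 + 18.6 = 47 for KD025-208 and 7.9 + 18.6 = 26 for KD025-213. Companion Study adults can enter after 6 months of treatment, so the effect is larger for them. The withdrawal rates are high: KD025-213 had 3/86.9 = 3.5% per year.

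**6. Forces in the other direction**
- LTFU stops at the FFS event (Protocol 6.2.5). At death hazard 0.09, with an FFS hazard of 0.2 per year and death hazard doubled afterwards (assumptions), true 36-month OS is 71.7% but 75.6% is estimated even under the SAP rule: +3.9 points.
- OS runs from first belumosudil dose, in subjects who had to be alive to enrol. With entry at 12 to 30 months (assumption), 36-month OS reads 89% instead of 76%.

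**The case against.** The strongest case against is that this is small and descriptive. The study has no hypothesis and no power calculation. Quarterly visits and LTFU contacts keep the usual gap below 3 months, and subjects who entered from parent-study LTFU have no 28-day visit to lose. The 140-day gap needs an unusual sequence. Day imputation applies only when the day alone is missing, and the SAP chose it as the conservative option.

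Most of this stands as to size. It does not rescue the rules. Being conservative does not justify a date that the record rules out. SAP 3.1.6.1 requires imputed adverse event and medication start dates to be sensible, and event dates have no such check. LTFU information may come by telephone, mail or medical records, so partial dates are plausible.

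A reader might infer two stronger things:
- **Reported OS will be too low overall.** The documents do not support this. Ending LTFU at the FFS event can push OS up if risk then rises, and requiring survival to enrolment pushes it up, by as much as these rules push it down or more.
- **The plan brings in public-record deaths one-sidedly.** It does not say so. Protocol 4.6 is permissive, covers withdrawal of consent rather than loss to follow-up, and is not limited to deaths; the SAP is silent. Losses of 2 to 5 points arise only if withdrawal can begin at first dose and runs at 10% to 20% per year.

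**Conclusion.** Two stated rules give wrong dates. The censoring rule discards documented event-free time at the 28-day visit while counting events in the same interval. The imputation rule can place an event before a visit that documents its absence, and can make DOR negative. Both follow from the text without assumptions.

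Their size does rest on assumptions. The censoring rule alone lowers 36-month OS by about 0.1 to 0.3 points, or 0.5 to 1.2 with a missed contact, for death hazards of 0.05 to 0.15 per year. Deaths-only use of public records is possible but not prescribed. It would take off under 1 point more if entry is near month 24, and more for earlier entrants. The net direction of OS bias is not established.

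**What to change.** - **SAP 3.7.2.5:** censor OS at the last date known alive from any source, including the 28-day visit, laboratory tests, ECG, adverse event records, dosing and any contact.
- **SAP 3.7.2.3 and 3.7.2.4:** censor TTNT and FFS at the last date documented event-free for that endpoint's own components. The 28-day visit counts where it records them. It records cGVHD therapies, which serves TTNT; for FFS, relapse status must also be documented, and Protocol 6.2.4 does not list it.
- **SAP 3.1.6.2:** set an imputed event date to the later of the 1st of the month and the day after the last documented event-free date, but no later than the last day of the recorded month. In the example above this gives 21 June. Without the cap, an event recorded as June in a subject event-free on 30 June would move to 1 July.
- **Public data:** state in the SAP that public vital status is either sought for all withdrawn subjects to one common date, where permitted, with those not found dead censored at that date, or used for none.

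The cost is SAP wording and programming. A public-record search is optional, but if done it must cover every withdrawn subject.
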